In summary, throughout the implementation of these and other studies, we have substantial experience conducting large-scale and complex randomized clinical trials in perinatal health and iron status among pregnant women in Tanzania. Of particular importance to the current proposal is the demonstration that we can enroll large numbers of pregnant women into large-scale clinical trials, and achieve high rates of follow-up and adherence after fully informed consent. Our findings highlight the burden of clinical complications associated with iron deficiency and malaria and provide support to the importance of examining the effect of the safety and efficacy of iron supplementation in the context of high malarial burden, and examining immunological and clinical outcomes related to malaria in pregnancy.

Research Design and Methods

Eligibility criteria: Participants will be recruited from pregnant women presenting to a large prenatal care clinic in Dar es Salaam, Tanzania. More than 90% of women present for their first prenatal care visit after the 12th week of gestation. Eligible participants will be pregnant women at or before 27 weeks of gestation, who are primigravida or secundigravidae, not anemic (defined as Hb<8.5 g/dL) or iron deficient (defined as serum ferritin <12 μ g/L), HIV-uninfected, and intend to stay in Dar es Salaam until delivery and for at least six weeks thereafter. Women with high iron stores at baseline (i.e., serum ferritin >200 μ g/L) will be excluded. HIV-infected women will be referred for standard of care services, including provision of antiretroviral treatment, as needed. The recruitment process will be completed within one week, such that randomization will be completed at the latest by 20 weeks of gestation.

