Recruitment of Study Participants: Recruitment will take place at Amtulbai clinic in Dar es Salaam in order to expedite enrollment of the desired sample size, 1500. This center was selected as it provides antenatal services to a large number of pregnant women in Dar es Salaam, and reflects a high malarial burden in its patient population. We maintain adequate clinic space and have an excellent working relationship with physicians and nurses there. (*a) First visit:* A brief baseline questionnaire and clinical assessment will be administered to every woman presenting for prenatal care and who satisfies the eligibility criteria above. A specimen will be collected at baseline to assess iron status, including serum ferritin and hemoglobin levels, and sent to the lab for testing. They will have the study objectives and design explained to them and pre-HIV-test counseling will be provided to all women as per standard of prenatal care in Tanzania. Issues of confidentiality of the result will be underscored. Blood will be tested using two rapid HIV assays, with confirmation of discrepant results using ELISA as per national guidelines. Results will be available on the same day. Women will be informed of the result of HIV testing and post-test counseling will be provided. Eligible women will be asked to come back 3 days later for confirmation of gestational age, and for results on their iron status, including hemoglobin levels and serum ferritin. Women with HIV infection, severe anemia (Hb < 8.5 g/dL), and/or low iron status (serum ferritin $< 12 \mu g/L$) as well as women with evidence of iron overload (ferritin > 200 µg/L) will be excluded from participation, and will receive standard prenatal care services including antiretroviral therapy and iron supplementation, as needed. (b) Second visit: The period between the first and second visit will allow mothers to consider the matter of participation in the study further, thereby reducing the number of defaulters once randomization of the subject has taken place. At this visit, eligibility will be assessed. Written informed consent for participation is the trial will be sought. Consented mothers will have a detailed background questionnaire administered and a full clinical examination will be carried out. Women will be randomly assigned to one of the experimental regimen groups below. Each mother will receive a one-month supply of capsules, and will be given an appointment to come back a month later. They will be escorted home by one of the project staff to record the exact location of the house that will be visited, if necessary.

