
Experimental Regimens and Randomization Procedures: Women will be randomly assigned to receive a daily oral dose of one of the following two regimens from enrollment and until delivery: (a) 60 mg iron (as ferrous sulphate) or (b) placebo. Tablets will be packaged in identical coded bottles that contain supply for 45 days (although the research visits are scheduled at monthly intervals, the extra tablets are necessary in case a woman is delayed in coming in for her scheduled visit). A list from 1 to 1500 will be prepared according to a randomization sequence in blocks of 20. Each of the two study clinics where randomization will occur will have a subset of the list of numbers. At enrollment, each eligible woman will be assigned to the next numbered bottle of regimen at that site. Experience has shown that unblinding, whether real or based on an impression or perception that develops among subjects or staff, is more likely to occur if regimens are color-coded or bear simple numeric codes. To minimize this risk, we will provide the regimen in bottles labeled with the participant's identification numbers, and will make active tablets and placebo indistinguishable, so that neither the subjects nor the investigators can identify which group of subjects is randomized to the same regimen.

The proposed dose of 60 mg elemental iron (200 μ g ferrous sulphate) is the WHO-recommended dose for universal supplementation during pregnancy. It also corresponds to the WHO-recommended dose for daily supplementation over a 3-month period among lactating women and women of reproductive age who live in areas where the prevalence of anemia exceeds 40% [84]. Although the prevalence of anemia among women of reproductive age exceeds 40% in Tanzania [33], the WHO-guidelines during lactation and reproductive age have not been adopted by the Tanzanian Ministry of Health and this practice is thus currently not in use [84].

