High-dose iron supplements can cause gastrointestinal side effects, such as upper abdominal discomfort, nausea, and constipation [112], and can inhibit the absorption of zinc [114]. These side effects can be associated with non-adherence, as well as poor dietary intake of other important nutrients. The Institute of Medicine determined the Lowest-Observed-Adverse-Effect Level as 70 milligrams of iron per day, based on studies that identified minor gastrointestinal symptoms occurring at daily intake of 11 milligrams of iron from diet and 60 milligrams of iron from supplementation [73]. The Tolerable Upper Intake Level with no expected adverse effects was identified at 45 milligrams of iron per day among adults, including pregnant women [73]. At

the 60 milligram dosage recommended by the World Health Organization, minor side effects include epigastric discomfort, nausea, diarrhea, and constipation [73]. However, any minor side should be mild in the vast majority of cases, and will be monitored closely throughout follow up. In addition, the dosage is commonly used worldwide among pregnant women in many developing countries.

Follow up Schedule: Each pregnant woman will be seen at one of the two study clinics once a month until delivery. At each visit, trained attendants will administer a questionnaire on the health of the woman in the preceding month, and a medical officer will carry out an obstetric examination. At the end of her monthly visit, every woman will be given a month's supply of capsules. Adherence in the previous month will be assessed through questioning of the mother, capsule count, and measurement of plasma serum ferritin levels in a random sub-sample of women (see section on Adherence below).

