Women who do not come for their monthly appointments will be visited at home when possible and asked to come to the study clinic if their health status allows. One of the eligibility criteria for the trial is a woman's intention to stay in Dar es Salaam until delivery and for six weeks thereafter. However, for women who do travel outside of Dar es Salaam, we will attempt to maintain contact with neighbors and relatives in the area to collect information on the outcome of pregnancy, and women will be asked to deliver at the same hospital where they are being followed up (**Amtullabai** clinic). Study midwives will be available 24 hours per day to attend to study women, document details of delivery, and schedule post-natal appointments. We will keep a record of the Expected Date of Delivery, and if the participant does not come to the study clinic or present in labor up to three days after her due date, she will be visited at home; if she was found to have given birth, the child will be examined by the visiting nurse, and the mother will be encouraged to come to the study clinic for a complete examination by a study pediatrician. If the participant has complications during pregnancy or delivery and needs to be referred to either Temeke Hospital or Muhimbili Hospital, one of our study nurses will accompany the participant to the respective hospital.

After delivery, mothers will be given a clinic appointment at 6 weeks post-partum, in order to ascertain survival status, and to collect limited morbidity data and anthropometric measurements on mother and child. Clinical history (including the signs of malaria infection) and medications used by mother and child in the prior 6 weeks will be ascertained. General physical examination of mother and child, including the respiratory, lymphatic systems, skin, and central nervous system will be undertaken. Child measurements of length, weight, head circumference, chest circumference, and mid-upper arm circumference will be performed.

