Placental Malaria Infection: We will compare the proportions of randomized women who have placental malaria infection in the iron group, compared with women on placebo. To test the statistical significance of any difference observed we will use the χ^2 test. There are numerous risk factors for placental malaria which will be measured in this study at baseline (defined as the time of randomization), including maternal body mass index, gravidity, maternal mid upper arm circumference, hemoglobin, gestational age, maternal age, parity, and indicators of socioeconomic status as measured by education, occupation, possessions, and marital status. Although randomization ensures that, on average, treatment groups will be balanced with respect to all of these risk factors, this may not be true in the particular instance of the current study. Thus, we wish to assess the success of randomization by first comparing the baseline characteristics of women in the treatment groups using χ^2 and t-tests and then using multivariate modeling techniques such as logistic regression to identify the strongest independent imbalances. Then, we will re-assess treatment effects as observed in the original intent to treat analysis after adjusting for the risk factors associated with the strongest imbalances. A logistic regression model will be used for this analysis. We will compare treatment effects estimated from the original analysis to those obtained from the adjusted analysis to decide whether adjustment is necessary. Because placental malaria is not likely to be a rare event in this study population, the odds ratio may not be a good approximation to the parameter of interest, the risk ratio. Multivariate regression models for the risk ratio are now available in commercial software, and we will apply binomial regression models with the log and identity link functions to the data as well. Linearity of multiple risk factors on one scale, e.g. the logistic, generally implies that there will be interactions of these risk factors on another scale, e.g. with the identity link. Goodness-of-fit of the data to various models forms will be explored, and interactions reported.

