
• Accrual: Recruitment will take place at a large prenatal clinic. This will require a good organizational and supervision system. We have used a system of similar complexity to screen approximately 40,000 women every year as part of previous and ongoing perinatal/child health trials.

• Retention: A major limitation in large trials is the operational difficulty in following up subjects for long periods of time. We have experience with studies of similar design in Tanzania in which we instituted a package of non-coercive incentives for patients to continue coming for follow-up. As a result of these procedures we are able to achieve follow-up rates of 85-95%.

• Bias: The potential for observation bias exists in intervention studies such as this one if the researchers are aware of the experimental regimen to which a subject has been assigned. To avoid the researchers' assessment from being influenced by the regimen received, this will be a doubleblind study such that during the study neither the investigators nor the study subjects will know what each regimen contains.

• Adherence: We recognize that non-adherence decreases the statistical power of a study to detect any true effect of the regimens. Our power calculations show adequate power even after realistic amount of non-adherence. In addition, we intend to perform statistical analyses to adjust for non-adherence. During the implementation of the study, we will monitor adherence by questioning the subjects, by pill count, and by measurement of plasma serum ferritin levels in a sub-sample of subjects. We will attempt to maximize adherence of the study subjects by providing counseling and allowing the patients adequate time to think through the issues during the recruitment phase, thus eventually selecting a study population that is interested and reliable. Furthermore, we believe that the set of incentives we will provide, as discussed above, will reduce non-adherence.

• Capacity: Research in many developing countries is limited by the lack of well-equipped laboratories and well-trained research staff. Tanzania is one of the exceptions since a number of research projects with substantial laboratory and field research components have been implemented. Several of these studies have been carried out as collaborative efforts between Harvard School of Public Health and Muhimbili University of Health and Allied Sciences.

Summary

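### The protocol describes one recruiting clinic in some sections and two randomising clinics in others; if two is right, the primary analyses should be stratified by clinic, for a small gain

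*Protocol*

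**What the plan says.** The sections of the protocol divide as follows.

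- **One clinic.** Eligibility criteria: "Participants will be recruited from pregnant women presenting to a large prenatal care clinic in Dar es Salaam, Tanzania". Recruitment of Study Participants names a single clinic and justifies that choice in the singular: "Recruitment will take place at Amtulbai clinic in Dar es Salaam in order to expedite enrollment of the desired sample size, 1500". The Accrual item under Limitations: "Recruitment will take place at a large prenatal clinic". Follow up Schedule adds that "women will be asked to deliver at the same hospital where they are being followed up" and names one clinic in brackets, apparently the same one with a slightly different spelling.
- **Two clinics.** Ascertainment of Gestational Age places ultrasound at two proposed clinics. Experimental Regimens and Randomization Procedures: "Each of the two study clinics where randomization will occur will have a subset of the list of numbers". Follow up Schedule: "Each pregnant woman will be seen at one of the two study clinics once a month until delivery". The pharmacy text also speaks of study sites in the plural.

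The randomisation section describes one list, numbered 1 to 1500, in blocks of 20. The list is divided between the clinics, and each woman receives the next numbered bottle at her own site.

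Under Data Analysis, the main comparison for placental malaria is "We will compare the proportions of randomized women who have placental malaria infection in the iron group, compared with women on placebo", tested by chi-square. Parasite density, change in haemoglobin and birth weight are each tested by a two-sample t-test and a Wilcoxon rank-sum test. Clinic is not among the baseline factors listed, and adjustment is planned only for the factors with the strongest imbalances.

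**The concern.** The two descriptions cannot both be followed. The randomisation paragraph decides how the numbered bottles are divided and handed out. From the text, nobody can tell whether 1500 numbers run in sequence at one site or are split between two.

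A second point applies only if there are two clinics. Blocked allocation would then run within each clinic, and the usual principle is to analyse by the groups within which allocation was restricted. The planned tests do not. The imbalance-driven adjustment would not reliably bring clinic in, because a factor balanced by design shows no imbalance, however strongly it predicts malaria. At stake are standard errors that are slightly too large, and a list whose blocks may not survive the division between sites.

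**Working it through.** **1. Number of clinics.** This needs only the sections side by side. Eligibility, recruitment, the delivery arrangement and the accrual limitation give one. Ultrasound, randomisation and monthly follow-up give two. Follow up Schedule contains both readings. All of this is current text. The Time Schedule's fallback of asking other centres for referrals does not explain the difference, since referral does not create a second randomising site.

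**2. The list.** 1500 / 20 = 75 blocks, and 75 / 2 = 37.5. Equal subsets of 750 would therefore cut one block. The protocol does not say that the subsets are equal, or that they consist of whole blocks.

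Suppose one block is cut 10/10. The number X on iron in one half has P(X = k) = C(10,k)² / C(20,10), with C(20,10) = 184,756, and the imbalance is |2X − 10|.

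- All ten in one arm: 2 / 184,756, about 1 in 92,000.
- Imbalance of 2 or less: (63,504 + 2 × 44,100) / 184,756 = 0.82.
- Expected imbalance: about 1.7 women.

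**3. Information lost on placental malaria.** Assume two clinics of equal size with risks a and b and mean m. The fraction retained by an unstratified test is [a(1−a) + b(1−b)] / 2 divided by m(1−m).

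- 20% and 30%: 0.185 / 0.1875 = 0.987, a loss of about 1%.
- 10% and 30%: 0.150 / 0.160 = 0.94, a loss of about 6%. The standard error is too large by √(0.160/0.150) = 1.03, or 3%.

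**4. Type I error and power for placental malaria.** Inputs: 675 per arm (1500 less 10%, halved); mean placebo risk 25%, the middle of the protocol's 20-30%; two-sided 0.05; risk ratio 0.75 for power; 200,000 simulated trials per row, with 1:1 allocation within two equal clinics.

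| Clinic placebo risks (assumed) | Type I error, chi-square | Type I error, stratified | Power, chi-square | Power, stratified |
|---|---|---|---|---|
| 25% / 25% | 0.051 | 0.051 | 79.5% | 79.5% |
| 20% / 30% | 0.048 | 0.050 | 79.5% | 79.9% |
| 15% / 35% | 0.044 | 0.050 | 79.8% | 81.1% |
| 10% / 40% | 0.037 | 0.050 | 80.8% | 83.6% |
| 5% / 45% | 0.027 | 0.050 | 81.8% | 86.8% |

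The protocol's own table gives 57% for a 25% placebo rate and a ratio of 0.75. Read as a risk ratio, that cell does not reproduce. This is a separate matter and does not affect a comparison of two tests on the same inputs.

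**5. Continuous endpoints.** The protocol's table reproduces at 675 per arm. The minimal effects are 8.47% for density (stated 8.5%), 5.08% for haemoglobin (5.0%) and 1.98% for birth weight (2.0%). Power for a 5% haemoglobin change is 78.7% (79%).

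Now let the clinics differ, taking the tabulated SD as the within-clinic SD.

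- Birth weight, clinics 200 g apart (assumed): pooled SD = √(400² + 100²) = 412.3. The effective critical value is 1.96 × 412.3/400 = 2.02, so the true type I error is 0.043. For a 2% effect (61.7 g), power is 79.2% without a clinic term and 80.8% with one.
- Haemoglobin, clinics 1.5 g/dL apart (assumed): pooled SD = √(3.8² + 0.75²) = 3.87 and type I error 0.046. For a 5% effect, power is 77.6% without and 78.7% with a clinic term.

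**The case against.** The best reply is that one clinic is the likelier reading. Only one is named, its selection is explained in the singular, and a second is never identified. The two-clinic phrases may be residual wording. If so, everything about stratification and blocks falls away. That is a fair reply, and it is why the analysis part is conditional here. It does not remove the contradiction, because the two-clinic version sits in the randomisation instruction itself.

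The second reply is that a site term is often left to an analysis plan, and that the list of baseline factors is introduced as examples and does not exclude clinic. This stands in part. However, the protocol does fix the primary tests, and it fixes them without clinic.

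The third is that the effect is negligible. Both sites would be antenatal clinics in one city, and within the protocol's own 20-30% range the loss is about 1%. This stands. The 6% figure needs a 10% versus 30% contrast that appears nowhere in the protocol.

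The fourth is that a cut block is not implied. This also stands: the text is compatible with whole blocks, and an unfinished last block at either site would have a similar effect.

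**Conclusion.** The contradiction on the number of clinics is real and needs an editorial correction. The analysis point holds only if two clinics are confirmed, and it is then a small improvement. Information lost is about 1% at clinic risks of 20% and 30%, and about 6% at 10% and 30%. The power cost for placental malaria is 0 to 3 percentage points for contrasts up to 10% versus 40%, and 5 points at 5% versus 45%. All of these rest on assumed clinic differences and equal-sized clinics.

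A reader might infer three stronger things that the documents do not support.

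- **That the planned tests are invalid.** They are not. Leaving out a factor balanced by design makes them conservative, with type I error at or below 0.05 apart from simulation noise.
- **That each clinic has its own randomisation list.** The text describes subsets of one list.
- **That a block will be cut and leave ten extra women in one arm.** Equal subsets are nowhere stated. Even with a 10/10 cut, an imbalance of ten has a chance of about 1 in 92,000, and about 1.7 is expected.

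**What to change.** State the number of recruiting and randomising clinics once, and bring the eligibility, gestational age, recruitment, randomisation, follow-up and accrual text into line with it.

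- **If one:** delete the two-clinic wording. No stratification is needed.
- **If two:** name both, and state that each receives whole blocks of 20 (for example 37 and 38 of the 75). Make the primary analyses clinic-stratified: a Mantel-Haenszel test and risk ratio for placental malaria; a clinic term in the linear models for density, haemoglobin change and birth weight; and a van Elteren test in place of the plain Wilcoxon.

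The cost is a few sentences and one stratification factor. No extra data or participants are required.

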Preparation of regimen will always be conducted by two pharmacy staff members at Central Pharmacy. Regimen is prepared at the rear of the pharmacy during the less-congested hours of pharmacy operation, so that there is minimal disturbance to pharmacy activities. Pharmacy staff will prepare the study regimen by labeling coded bottles with the appropriate client ID number and name based on the master randomization list. The regimen will then be transported to the clinic staff by Monday morning for delivery to the sites *via* project transportation.

Clinic staff will also return empty and used regimen bottles to Central Pharmacy by Friday afternoon each week.

Central Pharmacy staff will prepare two bottles of study regimen for all new participants. Labels for these study regimen bottles will include a printed ID recruitment and randomization number, and a blank placeholder for the participant's name. The RA will be responsible for requesting the study regimen for new participants, obtaining it from the clinic pharmacy, and writing the participant's name in the appropriate space on the regimen bottles.

Subsequent regimen bottles will be prepared for participants at a rate of one per month, and include preprinted participant ID numbers and names.

Clinic pharmacy and study staff will be responsible for maintaining a supply of two regimen bottles for each participant at the clinic at all times. Regimen bottles should be stored so that the client names and ID numbers are clearly visible. When a new regimen bottle is prepared and received for a participant, the pharmacy staff should store the newest regimen behind the other bottles, such that regimen bottles are administered to participants in the order they are received from Central Pharmacy and client names and ID numbers are clearly visible. This procedure will ensure that an additional bottle of study regimen is always available for participants, in case a client arrives early for a clinic appointment, or if there are any issues with transportation of study regimen.

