There are two study arms for MAL1: iron folate and placebo. The regimens arrive at the pharmacy with two different codes. The pharmacy staff is blinded similar to the rest of the research team. The pharmacy is responsible for assigning the codes to each participant using a randomization list created by the Boston data team. This procedure maintains study blinding, assuring the pharmacists are not aware of which code corresponds to the high and low multivitamin doses.

Participants in MAL1 will be randomized to receive either iron or placebo in a double-blinded manner. All clinic research and pharmacy staff must remain blinded to study regimen composition and intervention group membership throughout the duration of the study. The head pharmacist will be responsible for maintaining the master randomization list and preserving blinding of all study regimen procedures and intervention group membership.

Two pharmacy staff members are involved in assigning codes to the study participants and labeling, with a third person overseeing the process to ensure that it is done properly.

When used regimens are returned to the pharmacy, assigned non-pharmacy staff will take samples and use the randomization list to check retrospectively if any errors were made throughout the process. Findings will be recorded and reported on the appropriate forms on a weekly basis.

Accountability of the study product is held by pharmacy staff. Shipping invoices are stored at the main pharmacy. Actual compliance to study regimen are recorded by both pharmacy and clinical staff. The site pharmacy will store the Patient Study Drug Flow Chart Records.

Study regimen inventory will be conducted once every three months by two pharmacy staff members. The pharmacists will conduct this inventory independently, with tallied results compared afterwards. In the event of any discrepancies in inventory, pharmacy staff should recount the study regimen together, in order to obtain a final total inventory for the study regimen. Results of the study regimen inventory will be recorded in an updated log book stored at Central Pharmacy.

Pharmacy personnel will also conduct clinic site visits every Friday on a rotating basis, so that MAL1 sites will be visited at least once every two months. Pharmacy personnel will evaluate the

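### Supply under two codes, one per arm, lets pharmacy staff and return checkers sort women into the two groups, contrary to the Protocol's own blinding rule

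*Protocol*

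**What the plan says.** Two parts of the Protocol deal with how the regimen is coded.

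*Experimental Regimens and Randomization Procedures* warns that unblinding, real or perceived, "is more likely to occur if regimens are color-coded or bear simple numeric codes". Bottles are therefore to carry the participant's number, and tablets are to be indistinguishable, so that "neither the subjects nor the investigators can identify which group of subjects is randomized to the same regimen". This section also describes the bottles as identical and coded.

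*Pharmacy Procedures and Regimen Disposal* describes the supply chain:

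- "There are two study arms for MAL1: iron folate and placebo", and "The regimens arrive at the pharmacy with two different codes".
- "The pharmacy is responsible for assigning the codes to each participant using a randomization list created by the Boston data team".
- "Pharmacy staff will prepare the study regimen by labeling coded bottles with the appropriate client ID number and name", working from the master list.
- When used bottles come back, "assigned non-pharmacy staff will take samples and use the randomization list to check retrospectively if any errors were made".
- "All clinic research and pharmacy staff must remain blinded to study regimen composition and intervention group membership throughout the duration of the study".

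The sentence explaining how the pharmacy stays blind refers to high and low doses of a multivitamin. This trial has no such arms.

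**The concern.** With one code per arm, assigning a code to a woman is the same act as placing her in one of two groups. Whoever holds the list of codes knows the full partition of the trial and lacks only the label on each half. That is weaker blinding than the pharmacy section claims for its staff, and it is the situation the randomisation section sets out to prevent.

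At stake is how much one leak reveals. Under two codes, a single known allocation, or a confident guess from symptoms that cluster in one code, identifies both halves. The data most open to influence depend on what women report or what staff choose to do: reported fever in the maternal malaria definition, symptom histories at monthly visits, adherence counselling and co-treatment.

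**Working it through.** The Protocol gives no figure to reproduce here. The check is a comparison of passages followed by a count.

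**Step 1. Does one code equal one arm?** There are two arms and two codes, and the pharmacy section speaks of each code as corresponding to one regimen. So the mapping is one to one for the whole trial.

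**Step 2. Who can see the partition?**

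- Pharmacy staff: yes. They assign the codes from the list and label coded bottles by name and number. The head pharmacist keeps the master list.
- Non-pharmacy staff checking returns: yes, for the bottles they sample and through the list they use. Findings are reported weekly; the frequency of the checks is not given, and nothing bars these staff from participant contact or outcome data.
- Clinic staff and investigators: not established. Labels for new participants are described as carrying an identification and randomisation number and a space for the name, with no mention of the code. The Protocol does not say whether the supplier's code is removed, hidden or left visible. A check of used bottles for errors suggests that it can still be read.

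**Step 3. Is the blinding rule met?** The rule has two parts: blind to composition, and blind to group membership. Pharmacy staff can meet the first. They cannot meet the second while assigning one of two codes to each named woman. This conflict lies within a single section and does not depend on whether the codes count as simple.

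**Step 4. How much does one disclosure reveal to a holder of the code list?** Inputs: N = 1500 randomised (*Experimental Regimens and Randomization Procedures*) and c codes, assumed to be used equally often. One disclosed arm fixes every woman on that code, N/c. When c = 2 it also fixes the other code by elimination.

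| Supply | Calculation | Women decoded |
|---|---|---|
| 2 codes (Protocol) | 1500/2 + 1500/2 | 1500 |
| 4 codes (illustrative) | 1500/4 | 375 |
| 8 codes (illustrative) | 1500/8 = 187.5 | about 188 |
| 20 codes, 10 per arm (illustrative) | 1500/20 | 75 |
| No shared code | one number per woman | 1 |

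Only the first row describes the Protocol; the others are assumed alternatives. The count measures exposure, not bias.

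**Step 5. Which endpoints are exposed?** Placental malaria and parasite density come from smears and haemoglobin from an automated counter. *Laboratory Investigations* keeps all laboratory staff blind, including the pathologist. Birth weight is measured by midwives, but it is an objective reading. Maternal malaria, a secondary endpoint, needs reported fever within 72 hours as well as parasitaemia, so it is more open to influence.

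**The case against.** The case for leaving the text alone has real force.

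- **The two sections are not opposites.** The randomisation section itself speaks of coded bottles. It warns against colour codes or simple numeric ones, and nothing says the two supplied codes are of either kind. Its promise covers participants and investigators, not the pharmacy. This stands: the clash with that section is with its aim, not its wording. The clash with the pharmacy section's own rule is direct.
- **Decoding needs two things at once**, the code list and a disclosed arm. Nothing sends arm identity or side-effect data to the pharmacy, and the data safety monitoring board's closed reports are confidential. This also stands, and it makes the figure of 1500 conditional.
- **No pharmacy role in endpoint assessment is described**, and the primary endpoints are objective. This stands and limits the harm.

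A reader might go further and infer that clinic staff can see who shares a regimen. The Protocol does not establish that, because it is silent on whether the code is legible at the clinic. A reader might also infer two conflicting ways of allocating a regimen: the next numbered bottle at the site, or a code assigned by the pharmacy. These can be read as steps of one process. The pharmacy matches codes to numbers from the list and pre-labels bottles, and the research assistant then draws the next one.

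None of this answers the remaining point: staff whom the Protocol calls blind to group membership are handed the grouping.

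**Conclusion.** The point holds in a limited form. The pharmacy section does not deliver the blinding it requires: pharmacy staff, and the staff who check returns, can sort women into the two groups and lack only the knowledge of which group receives iron. For a holder of the code list, one disclosed allocation decodes 1500 of 1500 women. That figure assumes one code per arm throughout, as the text indicates, and a person who has both the list and the disclosure.

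The documents do not support the inference that the whole trial is open to anyone at the clinic who learns one woman's arm, or that the primary results are compromised. The exposure lies mainly in symptom-based malaria, adherence counselling and co-treatment. It deserves correction because the Protocol itself names the risk and the remedy is modest.

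**What to change.** 1. Reconcile the randomisation text with the pharmacy text so that both state the same blinding: who may see codes, who may see the list, and what each is blind to. Replace the carried-over multivitamin sentence, and settle whether the active arm is iron or iron with folate in that section.
2. Use several codes per arm, assigned at random within arm. With 10 per arm, taken as an illustration, pharmacy staff would still see sets of about 75 women on the same code but could not assemble the two arms, and one disclosure would stop at about 75.
3. State that the code is concealed on the bottle as dispensed, in a way that still lets the return check read it.
4. Restrict the list-based return check to a designated person with no participant, outcome or dispensing role.

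The cost is a labelling change before packing, some procedure wording, and more codes to track in the quarterly inventory. Design, sample size and analysis are unchanged. Having every bottle over-labelled outside the study team is not recommended: bottles are prepared monthly for each woman, so it is not clearly cheap, and removing the code altogether could defeat the Protocol's own check for labelling errors.
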